The primary outcome is completion of any CRC screening test (guaiac fecal occult blood test, FIT, sigmoidoscopy, or colonoscopy) within 12 months of randomization. The analytic approach taken will depend on whether or not an interaction exists between the outreach and inreach strategies on screening completion. If no interaction is present, screening rates for inreach vs. usual care and outreach vs. usual care will be compared using a Chi-square test of proportions, requiring $p < 0.01$ for statistical significance. If interaction is noted, we will compare screening rates with a Chi-square test of proportions for inreach without outreach vs. usual care, as well as inreach with outreach vs. usual care separately, using a $p < 0.025$ to indicate statistical significance. In both cases (interaction or no interaction), secondary comparisons will include inreach plus outreach vs. usual care, as well as inreach plus outreach vs. either strategy alone. We will conduct additional analyses treating screening completion as the dependent variable, and examine the relationship of group assignment, demographic characteristics, primary provider, and clinic visit frequency to this outcome. Factors associated with screening completion on univariate analyses will be considered as part of a logistic regression model examining factors independently associated with screening completion; in the case of interaction by group assignment a term for interaction will be included in our models. Additionally, interactions between other factors (e.g. gender, age, language preference, income, inreach strategy and frequency of clinic visits) will be considered.

Approach, Aim 2 Process Evaluation. Following the RE-AIM framework(41-43), a quasi-experimental process evaluation of intervention programs is proposed as part of the research protocol using validated measures developed in previous studies(44). This process evaluation is designed to examine the intervention’s acceptability, feasibility, and sustainability(45-47). Process measures include: intervention fidelity, recruitment and retention issues, dosage delivered and received, participant satisfaction, and *navigator* perceptions on areas for improvement in each one-on-one session. [name], [name], and [name] will lead trainings to ensure intervention fidelity and standardized intervention delivery and dosage.

Team Management Plan. The study team includes [name], [name], [name], [name], [name], and [name]. All have extensive experience with conducted research and promoting health among underserved populations. The research team currently has 2 NIH- funded and 1 ACS funded RCT studies at SYHC focusing on chronic disease, and cancer navigation (**see Biosketches**). Successful recruitment, intervention, and measurement methods and from these studies will be used in the proposed study for formal protocol development. The team will work collaboratively to set goals, timelines, and achieve study objectives. Drs. [name], [name], and [name] will lead the final prep to research work required for finalizing study interventions. [name] will lead planning and evaluation of Aim 1. [name] will serve as the lead biostatistician for analyses. [name] will lead the Aim 2 process evaluation. [name] will play a critical role in leading the execution of activities under Aims 1 and 2 at the SYHC setting, including day-to-day management of study activities and interventions. All investigators will participate in analysis, interpretation, and publication of results.

Threats to Validity. Contamination due to the potential exchange of information between the intervention groups is a recognized threat to the integrity of the proposed study design due to nature of the study setting. Evidence from our pilot work suggests this has not been an issue to date. The SYHC has over 90,000 registered patients that it serves in the target area. As recruitment proceeds, eligibility screening will include examining if family members are already participating in the proposed study. The staff selected for the interventions have comparable experience working within the community of interest, knowledge and training of selected topics to be covered during the navigation sessions, are bilingual (Spanish/English) and bicultural (Mexican-heritage). Findings would have external validity for other community health center settings, but limited validity to organizations that target middle and upper class populations.

Data Management and Quality Control. Data management will be an on-going activity designed to ensure the highest quality data possible. Activities include data-coding, computer data entry, data quality control and tracking, data confidentiality and development of data files for statistical analysis. Prior to data entry, forms will be examined for completeness and accuracy. A tracking system will be developed to ensure all forms have been administered to participants. Completed forms will be entered into the database using a double data entry verification system. All identified errors will be resolved using the original hard data. All corrected fields will be noted for a detailed audit trail. Forms will be kept in locked files at the SYHC. Subjects will be assigned study ID numbers to be linked with SYHC medical record numbers on data management and data analysis files. No identifiable information will be used in reports. Data entered and stored will be periodically archived on the secure SYHC server. Data entry and analysis will be performed on Pentium-based computers. Analyses will be carried out using SPSS and SAS by the study statistician ([name] at UCSD) who will receive a deidentified dataset from SYHC.

Timeline

Timeline (anticipated start date September 1, 2015)												
TASKS	Year 1				Year 2				Year 3			
	Q 1	Q 2	Q 3	Q 4	Q 1	Q 2	Q 3	Q 4	Q 1	Q 2	Q 3	Q 4
Weekly academic-community partnership team meetings												
Prep to research finalization of interventions												
Aim 1: Compare CRC screening rates associated with use of a) the inreach strategy, b) the mailed FIT outreach strategy (FIT outreach), c) inreach + FIT outreach, and d) usual care among n=648 individuals randomized across these groups.												
a. Random Assignment and Intervention (1/4 sample size per Q, Q1-4)												
b. Completion of 12-month follow up for outcomes												
c. RCT Analyses												
Aim 2: Process evaluation												
a. Process evaluation data collection												
b. Process evaluation data analyses												
Dissemination of results through community and academic conferences and publications, Preparation of subsequent grant applications												

Impact and Next Steps. Several outcomes are anticipated as a result of this work. First, we will optimize two interventions for increasing CRC screening among underserved populations, particularly low income Latinos. We will then conduct a rigorous randomized trial of these interventions, including an assessment of whether inreach and outreach interventions are complimentary (and perhaps even synergistic) for boosting CRC

screening among underserved populations. Locally, if successful, this program would be adopted into ongoing standard of care for patient preventive service utilization at SYHC. Integrated implementation is highly likely at SYHC because the program fits with the health center's strategic organizational restructuring to align with health care reform and the new "Patient-Centered Medical Home" initiative, which promotes patient-centered integrative care, patient empowerment, care coordination, and a deeper focus on meeting clinical preventive service guidelines for all patients. Regionally and nationally, we will disseminate findings, lessons learned, and best practices to key community groups, research experts, and policy-makers facilitated through meetings of our local Council of Community Clinics, the National Association of Community Health Centers, the California Colorectal Cancer Coalition, and national and international scientific organizations. Extramural grant applications to study impact of implementing our findings in usual practice will be proposed (particularly considering the large number of FQHCs based in San Diego County), along with grant applications designed to test novel and/or improved interventions for boosting screening informed by the results of our work. To inform public health policy, we also expect data from this and future work to be used for cost-effectiveness analyses of our intervention strategies for boosting screening, as well as to support funds for implementation of population-based screening programs to promote CRC screening.

RATIONALE FOR SDSU, UCSD, and SYHC COLLABORATION

The collaboration proposed for this proposal meets many of the ideal criteria specified in the U54 RFA.

First, we propose a hypothesis-driven cancer prevention outreach project focused on reducing disparities in CRC screening among low-income Latinos. Our proposal includes randomized trial that will allow for highly interpretable results, whether or not our hypotheses are correct. Setting the study at a FQHC ensures that the research is focused on an underserved population, but also increases the chances that findings might be implementable in other, similar settings across the nation.

Second, each of the partners (UCSD, SDSU, and SYHC) brings unique expertise and opportunities to the partnership. UCSD/Moores Cancer Center is represented by [name], a gastroenterologist with significant clinical expertise in CRC screening, as well as research expertise and experience in the use of randomized controlled trials to test intervention strategies for increasing screening among underserved populations. He is a member of the Reducing Cancer Disparities program at the Moores Cancer Center, and also plays a role in promoting awareness of screening disparities and implementation of strategies to address disparities at a national level, as exemplified by invitations to speak at scientific forums and publication of his work in high impact journals.

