Fifth, we will conduct our study using a randomized controlled trial design that will allow our study to not only determine whether inreach and outreach strategies can be effective, but also provide valuable data regarding whether there is an interaction associated with using inreach and outreach strategies combined. To date, there have not been randomized trials examining whether a combination of inreach and outreach might be synergistic for promoting CRC screening – such a combination might be required to achieve Healthy People 2020 goals for screening 70.5% of the population.

APPROACH

Conceptual Framework:

The conceptual framework proposed from this study stems from the Chronic Care model with emphasis on re-design of the clinical delivery system, decision support and enhance clinical information systems with an application to proactive promotion of clinical preventive services (Figure 1)(39).

Overview:

We propose a randomized trial of a) an inreach strategy, b) FIT outreach, c) the inreach strategy plus FIT outreach, and d) usual care for increasing CRC screening among individuals age 50 to 75, not up to date with screening served by the SYHC. In Aim 1, we will test the impact of these strategies on screening completion (alone and together) among individuals not up to date with screening at SYHC. The primary outcome will be screening completion, defined by completion of a CRC screening test (home fecal immunochemical test, home guaiac fecal occult blood test, sigmoidoscopy, or colonoscopy) within 6 months of randomization. We will assign 162 patients (n=648 total) to each group. In Aim 2, we will conduct a process evaluation to examine the interventions' reach, effectiveness, acceptability, feasibility, and sustainability following the RE-AIM framework.

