The EHR will be queried 4 times over a 1 year period. At time of each query 1/4 of the target sample will be identified and randomized, and have the assigned interventions initiated. Each group will be followed for 12 months for the primary outcome: completion of any CRC screening test (guaiac fecal occult blood test, FIT, sigmoidoscopy, or colonoscopy), measured by evidence of screening documented within the EHR. Thus, the total recruitment period will last 12 months, and the duration through completion of 6 month follow up of all patients will be 24 months. Measurements will include demographic information (race, ethnicity, sex, and age), number and location of health center visits, primary provider, and comorbid medical conditions. In secondary analyses, we will determine whether screening rates vary across these characteristics, and also assess whether for significant interactions between characteristics and intervention effects.

Analytic approach and sample size, Aim 1. We estimated the sample size for 5 comparisons (usual care vs. inreach, usual care vs. outreach, usual care vs. inreach + outreach, inreach + outreach vs. outreach alone, and inreach + outreach vs. inreach alone), assuming $\alpha = 0.01$ across all groups and power ≥ 0.8 . For these assessments, we assumed the following rates of screening on follow up among individuals not up to date at baseline: 10% for usual care, 25% for inreach, 25% for outreach, 45% for inreach + outreach combined. The 10% rate for usual care and 25% estimate for outreach were conservative assumptions based on our previously cited work (30). The 25% rate for inreach was a conservative estimate based on observations that inreach interventions such as patient navigation have boosted screening completion (among patients referred for colonoscopy) by 41 to 78%. Finally, the 45% rate for both interventions combined was considered the minimal clinically significant difference that would justify implementing two different interventions for increasing screening. Under these assumptions, we computed need for a sample size of $n=648$ patients ($n=162$ for each group) to have sufficient power for all primary comparisons of interest.

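### The primary outcome is defined with two different windows, 6 months and 12 months, and the plan does not say which governs

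*Combined protocol and SAP*

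**What the plan says.** The plan has one primary outcome, completion of any accepted colorectal cancer screening test, and gives its window in several places.

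- **APPROACH, Overview:** "sigmoidoscopy, or colonoscopy) within 6 months of randomization".
- **Identification of candidate patients and recruitment:** "Each group will be followed for 12 months for the primary outcome", with the outcome "measured by evidence of screening documented within the EHR".
- **Analytic approach and sample size, Aim 1:** "guaiac fecal occult blood test, FIT, sigmoidoscopy, or colonoscopy) within 12 months of randomization".
- **Timeline:** the outcome follow-up row is labeled as 12-month follow-up.

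The recruitment section also gives the study's length. On enrollment it says: "Thus, the total recruitment period will last 12 months". For the study as a whole, the same sentence gives this total: "the duration through completion of 6 month follow up of all patients will be 24 months".

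The sample size rests on assumed screening rates of 10% (usual care), 25% (inreach), 25% (outreach) and 45% (both). They are described only as "rates of screening on follow up among individuals not up to date at baseline", with no time point. Of their origin the plan says: "The 10% rate for usual care and 25% estimate for outreach were conservative assumptions based on our previously cited work". The SIGNIFICANCE section reports that earlier trial at one year.

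**The concern.** The text contains two definitions of the same endpoint, and no sentence ranks them. The conflict cannot be put down to one mistyped figure, because the 6-month figure appears twice: in the Overview's definition and in the sentence on study duration.

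The window decides who counts as a success, since a patient screened in months 6 to 12 changes category with the definition. Outcomes come from the electronic record over 12 months, so both versions will be available from one dataset. An analyst could report either as the prespecified primary result and cite the plan for it. A fixed primary endpoint is meant to rule that out.

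**Working it through.** **1. Which window fits the stated duration?**

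Total duration = month of last randomization + follow-up. The recruitment section gives 12 months of recruitment in four record queries over a year, and a total of 24 months. The start of the count is not stated; first randomization is the natural reading. The last query could fall at month 9 or month 12.

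| Last randomization | 6-month follow-up | 12-month follow-up |
|---|---|---|
| Month 12 | 12 + 6 = 18 | 12 + 12 = 24 |
| Month 9 | 9 + 6 = 15 | 9 + 12 = 21 |

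The stated 24 months is not reproduced with the 6-month label in its own sentence (15 to 18). It is reproduced with 12-month follow-up when the last patient enters at month 12.

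**2. Does the sample size identify the window?**

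The most demanding comparison is 10% v 25%, with alpha 0.01 (taken as two-sided) and power 0.80:

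n = [z(0.995)·√(2·p̄·(1−p̄)) + z(0.80)·√(p₁(1−p₁) + p₂(1−p₂))]² / (p₁−p₂)²

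With p̄ = 0.175, this is [2.576·√0.28875 + 0.842·√0.2775]² / 0.0225, which rounds up to 149. The continuity correction raises it to 162, the plan's figure. The other comparisons need fewer with the same correction: 43 per arm (10% v 45%) and 142 (25% v 45%).

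So 162 reproduces, but it does not settle the window because the rates carry no time point. The source trial's one-year figures were 12.1% for usual care and 40.7% for FIT outreach. The planning values of 10% and 25% are discounted from these, which points to 12 months without excluding 6.

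**3. How many outcomes are exposed?**

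If the planning rates are 12-month rates, expected completions are 162 × (0.10 + 0.25 + 0.25 + 0.45) = 162 × 1.05 = 170.1, about 170 of 648 patients. The documents do not say how many would fall in months 6 to 12, so the number could be anything from 0 to 170.

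**4. Power**

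The plan gives no 6-month rates, so the direction of any effect is undetermined. Illustrations at n = 162 per arm and two-sided alpha 0.01 (the 6-month rates are assumptions):

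| Rates compared | Power, uncorrected | Power, continuity-corrected |
|---|---|---|
| 10% v 25% (plan) | 0.84 | 0.80 |
| 8% v 20% (assumed at 6 months) | 0.71 | 0.65 |
| 5% v 22.5% (assumed at 6 months) | 0.98 | 0.97 |

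Power could fall or rise, so no power claim is made.

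**5. False-positive risk if the better window were reported**

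If each test holds its nominal level, the probability that at least one of two is significant under the null is at most the sum of the levels:

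- No-interaction branch: 2 × 0.01 = 0.02 per comparison.
- Interaction branch: 2 × 0.025 = 0.05 per comparison.

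The two windows share outcomes, so the actual risk is lower. It was simulated with 4 million trials per setting, 162 per arm, an uncorrected chi-square test and equal true rates. The share of 12-month completions reached by month 6 is an assumption.

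| Common 12-month rate | Share by month 6 | Risk at nominal 0.01 | Risk at nominal 0.025 |
|---|---|---|---|
| 10% | 50% | 0.0155 | 0.0419 |
| 10% | 80% | 0.0145 | 0.0352 |
| 10% | 90% | 0.0130 | 0.0316 |
| 25% | 50% | 0.0179 | 0.0432 |
| 25% | 80% | 0.0157 | 0.0375 |
| 25% | 90% | 0.0144 | 0.0339 |

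Hypotheses 1a and 1b suggest that arms might be pooled when there is no interaction. At 324 v 324 the risk at nominal 0.01 is again 0.013 to 0.018.

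**The case against.** The best defense is that the intended window is plain. The follow-up sentence, the analysis section and the Timeline row all say 12 months, and the 6-month figure sits in one overview sentence and one subordinate clause. On that view this is a drafting slip: the sample size is unaffected and the repair is a few words. The argument on likely intent is sound, and it is why 12 months is favored below. It does not remove the conflict, because the Overview sentence is an explicit definition of the primary outcome and the duration sentence repeats its figure.

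A second objection is that the 24-month arithmetic depends on the counting. Preparatory work precedes recruitment, and a six-month lead-in would give 6 + 12 + 6 = 24. With the last query at month 9, neither window gives 24. The Timeline's shading is not available to settle the point. This has some force, so the duration is supporting evidence only. But the recruitment section mentions no lead-in and derives its total from recruitment and follow-up. The same section also follows patients for 12 months for this outcome, so it disagrees with itself however the months are counted.

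Third, nothing in the plan proposes to report the smaller of two p-values. That is correct: the false-positive figures are a worst case that the present wording leaves open, not a prediction.

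**Conclusion.** The concern holds and must be fixed. The primary outcome has two incompatible windows, 6 and 12 months, and no text decides between them. The 24-month total contradicts its own 6-month label when counted from first randomization, and it agrees with 12 months if the last patient enters at month 12.

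An unknown share of about 170 expected completions would change status with the window, if the planning rates are 12-month rates. Selecting the better window after the fact would raise the per-comparison false-positive risk to no more than twice nominal, and to roughly 1.3 to 1.8 times nominal under the assumed timing. The sample size of 162 per arm is reproduced and not in question, and no power loss or gain is claimed. The weight of the text favors 12 months but does not establish it.

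**What to change.** Settle on one primary window before any outcome data are examined, and make every statement of it agree.

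**If 12 months (better supported):**

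- Change the window in the Overview from 6 to 12 months.
- Change the 6-month label in the recruitment section's duration sentence to 12-month, keeping the 24-month total.
- Label any 6-month result as secondary.
- Add one sentence to the sample size section saying that the 10/25/25/45% rates are 12-month rates.

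The cost is two wording edits and one sentence. Sample size and duration do not change.

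**If 6 months was intended:**

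- Change the follow-up sentence in the recruitment section, the outcome definition in the Aim 1 analysis section and the Timeline row.
- Recompute the total duration (15 to 18 months from first randomization, depending on the last query).
- Give the assumed rates a 6-month basis and recheck the sample size against it.

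This costs more, because two of the present rates come from one-year results.

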RCT inclusion/exclusion criteria. We will **include** individuals age 50 to 75 years, with one or more SYHC visits in the last year, at average-risk for CRC but not up-to-date with screening, insured by a MediCal provider, Medicare, or private health insurance. We will **exclude** individuals with personal history of CRC or colorectal polyps, as well as the uninsured. Uninsured individuals will be excluded because in absence of health insurance, we cannot guarantee that screening (and cancer care if CRC is found) will be financially possible. Inclusion and exclusion criteria will be applied through queries of the SYHC EHR.

Identification of candidate patients and recruitment. Using the SYHC EHR we will enroll and randomize 648 individuals meeting inclusion/exclusion criteria: 162 to usual care, inreach, mailed FIT outreach, and the

inreach strategy plus FIT outreach, respectively (see sample size and power calculations below). A waiver of documentation of informed consent will be obtained for randomization and intervention delivery based on two primary factors: 1) goal of increasing screening for as many individuals as possible, and 2) scientific advantage of observing as close to “real world” impact of the planned strategies on a sample of patients. We reviewed with our Institutional Review Board a potential strategy for complete waiver of informed consent, but were advised that maximizing patient autonomy and awareness of potential loss of confidentiality associated with research data collection merited at minimum a one-page informational research “fact sheet” that would provide patients with information about the research project. In the letter, patients will be the option to specifically note a desire not to participate in the intervention or subsequent data collection. Recruitment will continue until a sample size of 162 individuals per group who do not opt out of the research is achieved. In our primary, intent to screen analysis, we will analyze all randomized individuals who do not opt out of the research.

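### The primary intent-to-screen set drops randomized people who opt out, without saying whether someone who declines only the intervention counts as an opt-out

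*Combined protocol and SAP*

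**What the plan says.** All of the following is in the combined protocol and SAP, under Approach, Aim 1.

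- **Analysis set** (Identification of candidate patients and recruitment): in the primary analysis, "we will analyze all randomized individuals who do not opt out of the research".
- **Letter** (same section): patients have the "option to specifically note a desire not to participate in the intervention or subsequent data collection". Opting out of the research is not defined further. The reasons given for the fact sheet are patient autonomy and "awareness of potential loss of confidentiality associated with research data collection".
- **Numbers** (same section): "Using the SYHC EHR we will enroll and randomize 648 individuals meeting inclusion/exclusion criteria", and also "Recruitment will continue until a sample size of 162 individuals per group who do not opt out of the research is achieved".
- **Timing and outcome** (same section): at each of four EHR queries a quarter of the sample is identified, randomized and started on its assigned intervention. The primary outcome is "measured by evidence of screening documented within the EHR". No opt-out step before randomization is described.
- **Planning rates** (Analytic approach and sample size, Aim 1): "we assumed the following rates of screening on follow up among individuals not up to date at baseline", namely 10% for usual care, 25% for each single strategy and 45% for the combination, with alpha 0.01 and power of at least 0.8.

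**The concern.** An intent-to-screen analysis is meant to keep people in the arm to which they were randomized, whatever they do afterwards. Here some randomized people leave the primary set because of a choice that the plan places no earlier than randomization.

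For people who refuse use of their records, removal may be unavoidable, and the confidentiality reason for the fact sheet supports it. That reason does not extend to someone who declines only a mailed kit or a navigator. Such a person's outcome is in the EHR and needs no contact. They also belong to the population in the Overview, where "we will test the impact of these strategies on screening completion (alone and together) among individuals not up to date with screening at SYHC". Declining the offer is part of a strategy's real-world impact.

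Usual care has no assigned intervention to decline, although its patients can still refuse data collection. Opt-out could therefore differ between usual care and the active arms, in number or in kind, and the comparison would then no longer be between fully randomized groups. The direction is not fixed. The active arm is favoured if opt-outs are screened less often than others, and disadvantaged if they are screened more often. There is almost no bias if opt-out is equal across arms and happens for the same reasons.

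**Working it through.** **The plan's own figure.** Inputs: 10% vs 25%, two-sided alpha 0.01, power 0.80.
- Mean rate (0.10 + 0.25)/2 = 0.175.
- Uncorrected n = [2.576·√(2·0.175·0.825) + 0.842·√(0.10·0.90 + 0.25·0.75)]² / 0.15² = 148.4, so 149 per arm.
- With continuity correction, (148.4/4)·[1 + √(1 + 4/(148.4·0.15))]² = 161.5, so 162 per arm, and 4 × 162 = 648.

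The plan's figure reproduces exactly with the continuity correction. It contains no allowance for opt-outs. The plan names a Chi-square test without saying whether it is corrected, so both versions are given below.

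**Method.** The documents give no opt-out rate q, so 5%, 10% and 20% are assumed. If a whole arm has screening rate p and its opt-outs have rate d, those left in the analysis have rate (p − d·q)/(1 − q). Rejection probabilities come from exact binomial enumeration of the 2×2 chi-square test at 0.01, with 162 analysed per arm.

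**No true effect (10% in both arms).** With no opt-out, type I error is 0.95% (0.5% corrected).

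| Scenario | Result | q = 5% | q = 10% | q = 20% |
|---|---|---|---|---|
| (a) Opt-out in active arm only, none screened | Analysed active rate, 0.10/(1 − q) | 10.5% | 11.1% | 12.5% |
| | Bias (points) | +0.5 | +1.1 | +2.5 |
| | Type I error | 1.0% | 1.3% | 3.0% |
| | Corrected | 0.6% | 0.8% | 1.9% |
| (b) As (a), usual care opts out at q/2 | Bias (points) | +0.3 | +0.6 | +1.4 |
| | Type I error | 1.0% | 1.05% | 1.5% |
| | Corrected | 0.5% | 0.6% | 0.9% |
| (c) Opt-out in active arm only, opt-outs screened at 20% | Bias (points) | −0.5 | −1.1 | −2.5 |
| (d) Equal opt-out, same reasons | Bias (points) | 0 | 0 | 0 |

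In (a), type I error passes 2% only above about 15.5% opt-out (20.5% corrected).

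**True effect, reverse direction.** Planned power for 25% vs 10% with 162 per arm is 85% (81% corrected). If the whole active arm has 25% and its opt-outs 35%, the analysed rate is (0.25 − 0.35q)/(1 − q) = 24.5%, 23.9% and 22.5%. Power falls to 82%, 79% and 69% (78%, 74% and 63% corrected).

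**Numbers randomized.** Reaching 162 non-opt-outs per arm takes 162/(1 − q) = 171, 180 or 203 per arm, or 684, 720 or 812 in total at equal opt-out. Randomizing 648 and reaching 162 non-opt-outs per group agree only if nobody opts out.

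**The case against.** The strongest answer is that the letter may describe one combined opt-out from the research. The text speaks of a single option and then twice of opting out of the research. On that reading no intervention-only decliner can be identified, every opt-out has refused data use, and removing them is defensible. A reader might infer that the letter offers two separate refusals, but the documents do not establish that. What stands is that the wording covers both matters, the plan does not say which reading applies, and the analysis set depends on it.

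A reader might also infer that opt-out will be heavier in the active arms and that the trial is therefore biased towards the interventions. The documents do not support this. They do not say whether the letter differs by arm, whether it discloses assignment, or when it is sent relative to disclosure. The recruitment rule allows for opt-outs in every group. The asymmetry argument also does not carry over to the comparisons of the combination with a single strategy, where both arms have something to decline.

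The size is modest. In the one-sided scenario (a), corrected type I error stays below 1% at opt-out of 10% or less. In scenario (b) it stays below 1% even at 20%.

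Two further stronger readings fail. The 648 need not be a cap on randomization, since the recruitment rule already runs to 162 non-opt-outs per group; the tension is one of wording. Nor does the plan rule out counting opt-outs: Aim 2 covers reach and lists recruitment and retention issues as a process measure. It does not commit to counts by arm and type of refusal.

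**Conclusion.** The point holds as a minor, low-cost improvement. The plan states a rule that removes randomized people from the primary analysis. Read literally, the rule can remove people whose outcome is available and who need not be removed.

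Whether this would bias anything depends on facts that the documents do not give: how many opt out, whether that differs by arm, and how often opt-outs are screened. Under the assumed rates the bias runs from zero to 2.5 points in either direction, against planned differences of 15 to 35 points. Type I error is materially above 1% only if opt-out is both high and one-sided. In the reverse direction the cost is power. Without counts by arm and type, a reader of the results could not tell which case applied.

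**What to change.** 1. Define the primary set as everyone randomized, analysed in the assigned arm with EHR outcomes. Exclude only those who refuse use of their data, and state that people who decline only the intervention stay in.
2. If the letter has a single combined option, let patients mark the two refusals separately. This may need an IRB-reviewed wording change.
3. Report refusals by type and arm.
4. Add a sensitivity analysis that bounds the outcomes of data refusals in every arm and in both directions (none screened, and screened more often than the rest). It needs only the counts. One side of such a bound, at roughly the planned rates: 41/162 vs 16/162 gives p = 0.0003. Adding 9, 18 or 41 active-arm refusals as not screened (41/171, 41/180, 41/203) gives p = 0.0006, 0.0014 and 0.0070 (corrected 0.0011, 0.0023 and 0.0107, the last above 0.01).
5. Keep the rule of recruiting to 162 non-opt-outs per group, and align the sentence about randomizing 648 with it.

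**Cost.** Wording, two counts per arm, one sensitivity analysis and possibly a letter revision. There is some dilution if the planned 25% was meant only for people who do not opt out. Suppose all decliners are kept and screened at 10%, with 171, 180 or 203 randomized per arm. The active rate is then 0.25(1 − q) + 0.10q = 24.25%, 23.5% or 22.0%. Power is 84%, 82% and 78% against 85%, or 80%, 78% and 73% against 81% corrected; the corrected figure at 5% is 79.8%, just under the plan's 0.8. If randomization instead stopped at 162 per arm with decliners included, power would be 81%, 76% and 65% (76%, 71% and 59% corrected), which is why item 5 matters. There is no loss if the 25% already describes everyone not up to date at baseline, as the sample-size section words it.
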